7.6.1. Adverse Events

7.6.2. Definitions

Solicited AEs shown in the tables are extracted from the investigator assessment pages (CE) of the CRF. For unsolicited AEs, only the AEs within the 28-day period following each vaccination will be presented in the safety tables except for SAEs, which will be captured and tabulated in the outputs covering the whole study period. All other collected unsolicited adverse events will be presented through listings.

Solicited administration site symptoms will be considered as related to the study vaccine (by definition).

The severity of the AEs will be classified as grade 1 to 4. Solicited events that are graded less than grade 1, are not considered as AE. In case no grades are available, the grading of the solicited events will occur according to the grading list in Appendix 3.

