7.6.3. Analysis of Adverse Events

Number and percentage of participants with at least one particular AE (unsolicited/solicited) will be tabulated. Unsolicited AEs will be summarized by System Organ Class and Preferred Term. Solicited AEs will be summarized by class (administration site/systemic) and Preferred Term.

For solicited AEs following tables will be provided: summary, by worst severity grade, at least grade 3, related (systemic only), time to onset (in days) and duration (in days) for most frequent events and body temperature. Note: Duration is defined as number of days from the start of the event until resolution of the event. The time to first onset is defined as (date of first onset – reference date + 1). The reference date is the start date of the vaccination period.

^a As indicated previously, all analyses, including the safety analyses, will be conducted by actually received vaccine (“as treated” principle). The sentence “by study intervention regimens as designed per protocol” indicates that the statistical tables are designed with the planned vaccine regimens as columns. Therefore, participants who receive e.g. “Placebo, Placebo” instead of “Ad26.COV2.S 5x10¹⁰ vp, Placebo” will appear in the “Placebo, Placebo” column. However, to avoid sparse columns, participants who receive e.g. “Placebo, Ad26.COV2.S 5x10¹⁰ vp” (which is not a planned vaccine regimen) will be excluded from the statistical tables. They will be included in the listings, as well as in the programmed patient narratives where they will appear as “Subjects with vaccine misallocation”.

For unsolicited AEs, the following tables will be provided: summary table (including SAE, fatal outcome, and discontinuation), all events, most frequent, at least grade 3, permanent stop of vaccine, related, and SAE.

As a general remark, COVID-19 cases will be analyzed separately (see section [7.7.3](#)).

- SAEs that are COVID-19 related will not be included in the SAE tables, but will be included and flagged in the SAE listings. In MedDRA version 23.0, Preferred Terms (PT codes) “COVID-19 (10084268)”, “COVID-19 pneumonia (10084380)”, “Suspected COVID-19” (10084451), “Asymptomatic COVID-19 (10084459)”, “Coronavirus infection” (10051905), “Severe acute respiratory syndrome” (10061982), “SARS-CoV-2 carrier” (10084461), “Exposure to SARS-CoV-2” (10084456), and “Occupational exposure to SARS-CoV-2” (10084394) will be considered COVID-19 related AEs^a.

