- Adverse events that are not SAEs and are COVID-19 related will not be recorded in the SDTM AE domain, but rather in the SDTM CE domain.

Listings and/or participant narratives will be provided as appropriate, for those participants who die, discontinue study vaccinations due to an AE, or experience a severe or serious AE.

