7.6.7. Safety Analyses After Receipt of the Ad hoc Booster Vaccination

Study participants who receive the ad hoc booster vaccination, will be removed from the main safety analyses as of that point in time^a. A separate safety analysis will be conducted on the study

^a Note that participants may already have been removed from the main safety analyses due to unblinding and/or receipt of an unscheduled vaccine (either a COVID-19 vaccine received outside of the study or after crossing over from

participants who received the ad hoc booster vaccination, starting at the time of the ad hoc booster vaccination and showing their post ad hoc booster vaccination 7 day reactogenicity data, their post ad hoc booster vaccination 28-day unsolicited AE data, and their post ad hoc booster vaccination SAE/AESI data, as available. The statistical analysis will be descriptive. It will show study participants according to their original vaccination regimen in tables, listings and figures. In addition, the analyses may also be conducted separately by subgroups of study participants who received a COVID-19 vaccine outside of the study vs study participants who did not receive a COVID-19 vaccine outside of the study. A distinction between mRNA vaccines vs other vaccines may be made, if the numbers are sufficiently high. Otherwise, this information will be included in the listings only.

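### The 28-day limit on tabulated adverse events also cuts the tables of events that stop vaccination, so late non-serious events that stop a later dose are not counted there

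*SAP*

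**What the plan says.** SAP section 7.6.2 sets the tabulation rule for unsolicited adverse events: "only the AEs within the 28-day period following each vaccination will be presented in the safety tables except for SAEs". The exempt serious events are those "which will be captured and tabulated in the outputs covering the whole study period". For the remainder: "All other collected unsolicited adverse events will be presented through listings".

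Section 7.6.3 then names the tables for unsolicited events: "summary table (including SAE, fatal outcome, and discontinuation), all events, most frequent, at least grade 3, permanent stop of vaccine, related, and SAE". No time window is attached to the discontinuation row or to the permanent-stop table, and no AESI table is named. The same section provides listings and/or narratives "for those participants who die, discontinue study vaccinations due to an AE, or experience a severe or serious AE".

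AESIs enter the plan only in section 7.6.7, where the separate analysis after the ad hoc booster shows "their post ad hoc booster vaccination SAE/AESI data, as available". Apart from that, the term stands only in the abbreviation list.

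**The concern.** A 28-day window answers how often events arise soon after a dose. A table of events that stop vaccination answers a different question: which events kept participants from completing the regimen. Such an event can start at any time up to the planned date of the next dose, so a cut at 28 days removes part of the period in which it can occur.

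At stake is the count, by regimen and Preferred Term, of non-serious events that ended vaccination. That count bears on the tolerability of multi-dose and boosted regimens in a trial whose primary endpoints are safety endpoints. The table would carry a title suggesting completeness while omitting late events, and it could disagree with the disposition summary with nothing to explain the difference.

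**Working it through.** The plan states no figure to reproduce. The check is one of text, with one subtraction.

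**1. Which rule applies.** Section 7.6.2 limits the tables to 28 days and names one exception, serious events. The two discontinuation outputs in 7.6.3 are tables of unsolicited events with no window of their own, so the limit in 7.6.2 governs them.

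**2. Where a late event is placed.** Section 7.6.4 allocates an event to a period by its start date. In Table 1 (Cohorts 1a, 1b and 3) and Table 3 (Cohort 2b) of section 7.1.2, the post-dose 1 period ends at the latest 28 days after the dose, and Follow-up 1 then runs to one minute before dose 2. If dose 2 is never given, it runs to last contact or to the data cut-off. In Table 2 (Cohort 2a), Follow-up 1 runs to booster 1. An event that starts in any of these follow-up phases lies outside the 28 days.

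**3. Which events are affected.**

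| Event that stops a later dose | In the permanent-stop table and discontinuation row? |
|---|---|
| Starts by day 28, serious or not | Yes |
| Starts after day 28, serious | Exempt from the limit (COVID-19-related SAEs are kept out of the SAE tables by 7.6.3) |
| Starts after day 28, not serious | No; listing and/or narrative only |

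Under combination rule 3 in 7.6.4, a later record that continues an event of the same Preferred Term begun in the active period is assigned to that active period. It is therefore counted, and the gap concerns new late onsets.

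**4. Length of the uncovered time before dose 2 in Cohort 2b.** The inputs are target days 731 (Cohort 2a, one-dose primary regimen) and 787 (Cohort 2b, two doses), given under Amendment 2 in Changes to Previous Versions. Both belong to a removed booster visit set 24 months after completion of the primary regimen.

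- Dose interval = 787 - 731 = 56 days.
- Uncovered time before dose 2 = 56 - 28 = about 28 days.

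**5. Before a booster.** Section 7.1.2 builds the SAE window that ends 6 months after the primary regimen from the post-dose periods plus their follow-up, and that follow-up ends at booster 1. This suggests a booster at about 6 months, and so a longer uncovered stretch than before dose 2. The SAP does not state the booster date.

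**6. What else records these events.** Section 7.2 counts participants who discontinued vaccination, by regimen, and gives reasons for termination. Section 7.6.3 gives listings and/or narratives. Neither yields a count of adverse events by regimen and Preferred Term.

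**The case against.** The best defence is that 28 days is the endpoint. Sections 7.3 and 7.5 define unsolicited events over 28 days after each vaccination, with serious events followed longer, and 7.6.2 tabulates what those endpoints define. That stands for the general window, which is not in dispute. It does not settle the two discontinuation outputs, whose purpose is not 28-day incidence.

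The second defence is that nothing is lost, because listings, narratives and the disposition summary keep these participants in view. This also stands, and it limits the weight of the point. Those sources do not replace the missing count.

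Third, section 7.1.2 introduces an Entire study period for some tables and gives SAE tables only as an example, and the Data Presentation Specifications may add detail. This leaves some room, but the wording of 7.6.2 is specific and names a single exception. At best the window is ambiguous, and that needs the same repair.

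Fourth, the 56 days are inferred from a removed visit and apply to Cohort 2b only. That is fair. The gap itself does not depend on the exact interval, only on the next dose falling more than 28 days after the last.

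A reader might go further and infer that AESIs are wrongly left out of the main tables. The SAP does not support this as a definite fault. It neither defines AESIs nor says that they were collected before the ad hoc booster, section 7.6.7 shows them only as available, and serious AESIs fall under the SAE exemption in any case. A reader might also fear that a rise in AESIs after the booster would be an artefact of the tabulation rule. The SAP plans a separate descriptive analysis there, and no before-and-after comparison.

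**Conclusion.** The point holds for non-serious events that start more than 28 days after a dose and stop a later dose or booster. Under 7.6.2 as written, they are absent from the permanent-stop table and the discontinuation row of 7.6.3. In Cohort 2b this leaves about 28 of an inferred 56 days before dose 2 uncovered, with a longer stretch likely before a booster.

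These are lengths of time and not event rates. The number of events affected is unknown and may be small or zero. Converting the booster gap into a percentage of missed events would not be justified, since the SAP gives no booster date and a share of calendar time is not a share of events.

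The AESI part is conditional: it matters only if the protocol, which is not at hand, collected AESIs during the main period. Overall this is a modest reporting gap, worth correcting because safety is the primary objective and the correction is cheap.

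**What to change.** Change the exemption in section 7.6.2 to: except for SAEs and AEs leading to permanent discontinuation of vaccination, which are tabulated for the whole study period. In 7.6.3, apply the Entire study period from 7.1.2 to the permanent-stop table and to the discontinuation row. Participants would still leave the main analysis at the points set out in 7.6.7.

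The cost is one sentence and a change of period in two outputs. The downside is that non-serious events after day 28 may be less completely collected; a footnote to both outputs can say so.

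Conditionally, if the protocol collected AESIs during the main period, add a table of AESIs by regimen and period to 7.6.3. It should use the same definition as the outputs under 7.6.7 and carry a footnote with the date on which collection began. If they were not collected then, one sentence saying so is enough.

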7.6.3. Analysis of Adverse Events

Number and percentage of participants with at least one particular AE (unsolicited/solicited) will be tabulated. Unsolicited AEs will be summarized by System Organ Class and Preferred Term. Solicited AEs will be summarized by class (administration site/systemic) and Preferred Term.

For solicited AEs following tables will be provided: summary, by worst severity grade, at least grade 3, related (systemic only), time to onset (in days) and duration (in days) for most frequent events and body temperature. Note: Duration is defined as number of days from the start of the event until resolution of the event. The time to first onset is defined as (date of first onset – reference date + 1). The reference date is the start date of the vaccination period.

^a As indicated previously, all analyses, including the safety analyses, will be conducted by actually received vaccine (“as treated” principle). The sentence “by study intervention regimens as designed per protocol” indicates that the statistical tables are designed with the planned vaccine regimens as columns. Therefore, participants who receive e.g. “Placebo, Placebo” instead of “Ad26.COV2.S 5x10¹⁰ vp, Placebo” will appear in the “Placebo, Placebo” column. However, to avoid sparse columns, participants who receive e.g. “Placebo, Ad26.COV2.S 5x10¹⁰ vp” (which is not a planned vaccine regimen) will be excluded from the statistical tables. They will be included in the listings, as well as in the programmed patient narratives where they will appear as “Subjects with vaccine misallocation”.

For unsolicited AEs, the following tables will be provided: summary table (including SAE, fatal outcome, and discontinuation), all events, most frequent, at least grade 3, permanent stop of vaccine, related, and SAE.

As a general remark, COVID-19 cases will be analyzed separately (see section [7.7.3](#)).

- SAEs that are COVID-19 related will not be included in the SAE tables, but will be included and flagged in the SAE listings. In MedDRA version 23.0, Preferred Terms (PT codes) “COVID-19 (10084268)”, “COVID-19 pneumonia (10084380)”, “Suspected COVID-19” (10084451), “Asymptomatic COVID-19 (10084459)”, “Coronavirus infection” (10051905), “Severe acute respiratory syndrome” (10061982), “SARS-CoV-2 carrier” (10084461), “Exposure to SARS-CoV-2” (10084456), and “Occupational exposure to SARS-CoV-2” (10084394) will be considered COVID-19 related AEs^a.
- Adverse events that are not SAEs and are COVID-19 related will not be recorded in the SDTM AE domain, but rather in the SDTM CE domain.

Listings and/or participant narratives will be provided as appropriate, for those participants who die, discontinue study vaccinations due to an AE, or experience a severe or serious AE.

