6. POPULATIONS FOR ANALYSIS

For vaccine studies, study intervention assignment will follow the as treated principle: all analyses (including safety, immunogenicity and efficacy analyses) will be analyzed by the actually received vaccine.

Population	Description
All screened participants (ALL)	The “all screened participants” set includes all participants that were screened, regardless of whether they were enrolled and/or randomized.
All randomized participants (ALL RANDOMIZED)	The “all randomized participants” set includes all participants that were randomized to one of the treatment groups.
Full Analyses Set (FAS)	The full analysis set will include all participants with at least one vaccine administration documented.
Per Protocol Immunogenicity Set (PPI)	The per protocol immunogenicity population will include all randomized and vaccinated participants for whom immunogenicity data are available excluding participants with major protocol deviations expecting to impact the immunogenicity outcomes. In addition, samples obtained after missed vaccinations or participants with natural infection occurring after screening (if applicable) will be excluded from the analysis set.
Per Protocol Efficacy Set (PPE)	The per protocol efficacy population will include all randomized participants having received at least 1 vaccination for whom efficacy data concerning endpoint measures are available. All efficacy analyses will be done according to the as treated principle (ie, actually received vaccinations).

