7.3. Primary Endpoint(s) Analysis

The primary endpoints in this study, are:

All participants in Cohorts 1, 2, and 3:

- Solicited local and systemic adverse events (AEs) for 7 days after each vaccination in the primary regimen
- Unsolicited AEs for 28 days after each vaccination in the primary regimen
- For the primary endpoint: Serious adverse events (SAEs) from the first vaccination until 1 year after the second vaccination for Cohorts 1 and 3, and until 6 months after the primary regimen for Cohort 2

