The following endpoints are defined to examine the immune response in vaccinated individuals after natural infection and to explore other potentially informative biomarkers (eg, those associated with more severe disease):

- Confirmation of SARS-CoV-2 infection by molecular testing
- SARS-CoV-2 neutralizing titers in serum measured by a VNA (wild-type virus and/or pseudovirion expressing S protein)
- SARS-CoV-2-binding antibodies measured by ELISA: Analysis of antibodies binding to the SARS-CoV-2 S protein
- Functional and molecular antibody characterization
- Analysis of gene expression by RNA transcript profiling

7.6. (Other) Safety Analyses

Safety analyses will be performed on the FAS. Continuous variables will be summarized using the following statistics, as appropriate: number of observations, arithmetic mean (mean), standard deviation (SD), standard error (SE), median, quartiles (Q1 and Q3), minimum and maximum. Frequencies and percentages (one decimal place) will be generated for categorical variables. No formal comparisons between groups will be provided.

Safety data will be analyzed by study intervention regimens as designed per protocol^a. In addition, safety data will be analyzed by intervention regimens as designed per protocol and participant seropositivity status at screening. Data will be presented by period (post Dose 1, post Dose 2, post Booster 1, and post Booster 2, as applicable) as well as over the entire regimen, and for Cohorts 2a and 2b over the entire primary regimen and over the entire booster regimen. Denominator for the percentages is the number of participants in the considered population and phase for a certain regimen (incidence per 100 participants/phase).

Exploratory analyses by age (e.g. 18-40 years and 41-55 years) may be performed in Cohort 2.

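### Vaccinated participants with an unplanned vaccine sequence are left out of the planned-regimen safety tables, although safety is to be analysed on the FAS

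*SAP*

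**What the plan says.** SAP section 6 defines the analysis set without any exclusion for misallocation: "The full analysis set will include all participants with at least one vaccine administration documented". The same section sets the as-treated rule, under which data "will be analyzed by the actually received vaccine". Section 7.6 states: "Safety analyses will be performed on the FAS".

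The footnote attached to 7.6 (printed within 7.6.3) explains how this becomes a table layout: "the statistical tables are designed with the planned vaccine regimens as columns". It treats two kinds of misallocation differently:

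- If the sequence actually received is itself a planned regimen, the participant moves to that regimen's column.
- If the sequence is not a planned regimen (the footnote's example is placebo then Ad26.COV2.S 5x10^10 vp), the participant "will be excluded from the statistical tables". The reason given is "to avoid sparse columns".

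For the second group the footnote adds: "They will be included in the listings, as well as in the programmed patient narratives", where they are labelled as misallocated.

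The primary endpoints in section 7.3 are solicited adverse events (AEs), SAEs and "Unsolicited AEs for 28 days after each vaccination in the primary regimen". Section 7.3.3 sends all of them to 7.6 for analysis.

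**The concern.** A table that leaves out vaccinated participants is not an FAS table, whatever its title says. Here the participants left out can be people who received active vaccine, and the tables affected carry the primary endpoints. The footnote makes no exception for the SAE, grade 3 or higher, related-event or by-period tables.

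An event after a genuine Ad26.COV2.S dose would then add nothing to a tabulated incidence, and the person would be missing from the denominator. Listings and narratives describe the event, but they give no rate. The footnote does not require the number excluded to be reported, so a reader comparing the safety-table denominators with the FAS count in the disposition table (section 7.2) could find a gap that the table does not explain.

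**Working it through.** **Texts side by side.**

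1. Section 6: being in the FAS requires one documented vaccination. A participant given placebo then Ad26.COV2.S qualifies.
2. Section 7.6: safety is done on the FAS, and the percentage denominator is the number in the population and phase for a regimen. That participant should therefore be counted somewhere.
3. Footnote to 7.6: the columns are the planned regimens, and that participant is in none of them.
4. Steps 2 and 3 cannot both be followed for this participant. Programmed as written, the footnote prevails, and the tables cover the FAS minus the participants with an unplanned sequence.

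**A comparison within the SAP.** Under section 7.6.7, recipients of the ad hoc booster leave the main safety analyses only from the time of that booster. The footnote has no such time limit: the participant is removed whole, including the period before the error.

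**Is deletion needed to avoid sparse columns?** No. A pooled active column is not sparse, and the SAP already pools active regimens for harm monitoring (7.7.2) and for vaccine efficacy (7.7.3).

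**Size.** The SAP states no figure for this point, so there is none to reproduce. The following is an illustration only.

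- Inputs: N = 860 active recipients, from the pooled calculation in 7.7.3; regimen columns of 50, 75 and 150, assumed; k excluded participants, assumed to be 1, 5 or 10.
- Worst case: all k excluded participants have the event and nobody else does. The table then shows 0/(N − k), where counting them would show k/N.
- Exact 95% limits (Clopper-Pearson). For zero events the upper limit is 1 − 0.025^(1/n).

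| N | k | Table as planned (upper 95% limit) | If counted (95% limits) |
|---|---|---|---|
| 860 | 1 | 0/859 (0.43%) | 1/860 = 0.12% (0.00 to 0.65) |
| 860 | 5 | 0/855 (0.43%) | 5/860 = 0.58% (0.19 to 1.35) |
| 860 | 10 | 0/850 (0.43%) | 10/860 = 1.16% (0.56 to 2.13) |
| 150 | 1 | 0/149 (2.45%) | 1/150 = 0.67% (0.02 to 3.66) |
| 75 | 1 | 0/74 (4.86%) | 1/75 = 1.33% (0.03 to 7.21) |
| 50 | 1 | 0/49 (7.25%) | 1/50 = 2.00% (0.05 to 10.65) |

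Each excluded participant with an event therefore moves a pooled incidence by about 0.12 points, and a column of 150 to 50 by about 0.7 to 2.0 points. The 860 is a cross-cohort total. Section 7.1.5 keeps analyses within cohort unless stated otherwise, so no safety table now planned has that denominator, and a within-cohort pooled column would be smaller and shift by more.

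**The case against.** The rule is disclosed. The footnote restates the as-treated principle, gives its reason and says where the data go. Safety is descriptive, with no formal comparison between groups, so no test or margin depends on these participants. Section 7.6.3 also provides listings or narratives, as appropriate, for deaths, discontinuations of vaccination due to an AE, and severe or serious AEs. All of this stands, and it limits the point to one about tabulated rates.

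A reader might infer more than the text supports:

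- *That the events disappear.* They do not. The sentence after the exclusion keeps these participants in the listings and in labelled narratives.
- *That every misallocated participant is dropped.* Only those whose sequence matches no planned regimen are; the others are moved to the column they fit.
- *That every safety table is affected.* The rule governs the planned-regimen tables. The ad hoc booster tables (7.6.7) are laid out by original regimen and do not restate it.
- *That the effect is known to be material.* The SAP gives no count of such participants and no regimen sizes.

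Disclosure does not remove the conflict. The plan still calls these FAS analyses, and individual reports do not replace a numerator and a denominator.

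**Conclusion.** The footnote conflicts with the FAS definition in section 6 and with the statement in 7.6 that safety is analysed on that set. Followed exactly, the plan undercounts active exposure, and any events that go with it, in the tabulated primary safety endpoints. The events remain visible one participant at a time.

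The overall effect is small if misallocations are few, which is likely but not documented: about 0.12 points per event on 860, and about 0.7 to 2.0 points in a column of 150 to 50. These figures rest on assumed column sizes and on the excluded participant having an event that nobody else in the column had. The practical risk is the rare serious event, where one case is the difference between zero and not zero. The point is worth correcting because the remedy is cheap. It does not undermine any inference in the plan.

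**What to change.** Keep the planned-regimen columns and amend the footnote to 7.6 as follows.

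1. Add one pooled any-Ad26.COV2.S column to the overall AE, grade 3 or higher, related and SAE tables. Include misallocated participants who received at least one active dose, and count their events from the first active dose. State whether the column is pooled within or across cohorts, since 7.1.5 defaults to within cohort.
2. In each safety table, footnote how many FAS participants fall outside the regimen columns and point to the misallocation listing.

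Moving participants between regimen columns period by period is not advised. After dose 2 the placebo-then-active participant still matches no planned column. After dose 1 the placement is ambiguous where planned regimens share a first dose.

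The cost is footnote wording and one column in a few tables. The pooled column mixes dose levels and one- and two-dose regimens, which limits its use for reactogenicity, and the regimen columns will not sum to it; both need a note. Placebo periods before a misallocated active dose would still be untabulated, but item 2 makes that visible. Section 7.7.1 repeats the exclusion for immunogenicity, so its footnote should be checked at the same time.
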